1 PROTOCOL SUMMARY

1.1 Synopsis

Protocol Title: A Two-part Phase IIa Randomised, Double-blind, Placebo-controlled, Dose-ranging, Multi-centre Study to Assess Efficacy and Safety of Inhaled AZD1402 Administered as a Dry Powder Twice Daily for Four Weeks in Adults with Asthma on Medium-to-High Dose Inhaled Corticosteroids

Short Title: Efficacy and Safety of Inhaled AZD1402 administered Twice Daily for Four Weeks in Adults with Asthma on Medium-to-High Dose Inhaled Corticosteroids

Rationale:

Asthma is a chronic, complex, and heterogeneous respiratory disease characterised by a range of pathogenic features including pulmonary inflammation, mucus hypersecretion, variable airway obstruction, and airway remodelling. Symptoms and airway obstruction can resolve in response to therapy or spontaneously, but participants remain at risk of severe worsening of their asthma (exacerbations). These asthma exacerbations can be life-threatening, can significantly impact the participant's quality of life, and result in significant healthcare costs.

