- v Sampling on Days 2, 6, 8, 10, and 12.
- w CRP must be done locally on Day -1 (may be performed on Day -2 for logistical reasons) to confirm eligibility as per inclusion criterion 26. It may be performed throughout the study in the event of AE/AESI as required to inform suspension/stopping criteria.
- x Blood samples will be analysed for IgE if potential drug related IgE response is observed in any participant; may be collected on Day -1 or Day 1 pre-dose.
- y PCR may be performed to confirm hepatitis B / hepatitis C status if required.
- z Blood samples for PK measurements will be collected for all participants. Timing of samples: Day 1 pre-dose (-60 min), 1, 2, 3 (\pm 10 min), 4, 6, 8 (\pm 20 min) and 12 h (up to 1h prior to the next dose, must be before the subsequent dose); Day 28 pre-dose (-60 min), 1, 2, 3 (\pm 10 min), 4, 6, 8 (\pm 20 min), and 12h (\pm 1 h; single dose of AZD1402 only on Day 28). Pre-dose on Days 2, 4, 6, 8, 10, 12, 14, 16, 20, 24 (up to 1 h prior to the next dose, must be before the subsequent dose), 29 (24 h \pm 2 h after Day 28 dose), 30 (48 h \pm 2.5 h after Day 28 dose), 32 (96 h \pm 2.5 h after Day 28 dose), 39 (\pm 6 days), and 56 (\pm 4 days). Part Ib only: Day 20, 4 h post-morning dose (\pm 20 min). The PK sampling timepoints may be amended based on results from Part 1a/b. An unscheduled PK sample may be collected in the case of AEs and / or unscheduled safety blood sampling.
- aa ADA sampling, pre-dose Day 1, Day 14, Day 20, Day 24 (Part 1b only) and Day 28 and on Follow-up/unscheduled visits. CCI [REDACTED]
[REDACTED] An unscheduled ADA sample may also be collected in case of AEs/AESIs and/or unscheduled safety blood sampling.
- bb Sample collection if consented only. If for any reason the sample is not drawn at Visit 3, it may be taken at any visit until the last study visit.
- cc All urine pregnancy tests will be done pre-dose.

dd SARS-CoV-2 serology at Screening, End of Trial and final Follow-up Visits; PCR is optional and may be performed centrally or at the local laboratory as clinically indicated and as per local guidelines for the duration of the study. Ad hoc nasal and/or throat-swab specimen is to be collected for the identification of a suspected respiratory infection during any visit. This may be performed locally, or if required by central laboratory.

ee May be performed on Day -2 for logistical reasons.

Table 2 Schedule of Activities Part 2

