x Blood samples for PK measurements will be collected in all participants pre-dose at each visit, including unscheduled visits. Intense sampling may be performed in approximately 25% of participants per treatment arm (for example, 20 subjects in the **Q**mg treatment arm). Timing of intense samples: Day 1: 1, 2, 3 (\pm 10 min), 6, and 8 h (\pm 20 min), Day 21 4 h post-morning dose (\pm 20 min) and Day 28 (last dose), 1, 2, 3 (\pm 10 min), 6, 8 (\pm 20 min), 24 (\pm 2 h), 48 (\pm 2.5 h), and 96 h (\pm 2.5 h; single dose of AZD1402 only on last day of dosing). PK sampling timepoints may be amended based on results from Part 1a/b. An unscheduled PK sample may be collected in the case of AEs and / or unscheduled safety blood sampling.

y ADA sampling, pre-dose Day 1, Day 14, Day 21, Day 28, and at the Follow-up Visits. An unscheduled ADA sample may also be collected in the case of AEs/AESIs and/or unscheduled safety blood sampling.

z Sample collection only if consented. If for any reason the sample is not drawn at Visit 3, it may be taken at any visit until the last study visit.

aa Proposed samples and times: Serum: Pre-dose Day 1, pre-dose Week 2, Week 4 and at Follow-up. **CCI** Pre-dose Day 1, and Week 4. **CCI** Pre-dose Day 1, Day 28, and Day 39. **CCI** Pre-dose Day 1.

bb All urine pregnancy tests will be done pre-dose. In case of a positive result, a serum pregnancy test will be performed.

cc SARS-CoV-2 serology at Screening; PCR is optional and may be performed centrally or at the local laboratory as clinically indicated and as per local guidelines for the duration of the study. Ad hoc nasal and/or throat-swab specimen is to be collected for the identification of a suspected respiratory infection during any visit. This may be performed locally, or if required by central laboratory.

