9.4.3.6 Immuno-biomarkers

Results on immuno-biomarkers (cytokines, CRP, and immunoglobulins including IgE) will be

presented descriptively by treatment, separately for each part.

9.4.3.7 *Electrocardiogram*

Descriptive statistics will be produced at each scheduled assessment timepoint for all quantitative ECG parameters for both absolute values and changes from baseline.

An analysis of potentially clinically significant ECG values on QT, QTcB, QTcF, QRS and PR interval and heart rate will be performed. The number of participants with potentially clinically significant ECG values will be tabulated across time and treatment. The criteria based on severity will be defined in the SAP.

Outlier with respect to QTcF will also be tabulated for the following categories:

- Absolute value > 450 msec
- Absolute value > 480 msec
- Absolute value > 500 msec
- Increase from baseline > 30 msec
- Increase from baseline > 60 msec

9.4.4 *Other Analyses*

9.4.4.1 *Pharmacokinetics*

Pharmacokinetic analysis for AZD1402 will be performed by PK analysis vendor on behalf of AstraZeneca Research and Development. Pharmacokinetic parameters will be derived using standard non-compartmental methods using Phoenix® WinNonLin® version 8.1 or higher (Certara). All descriptive statistics will be performed using SAS® version 9.4.

The PK parameters will be calculated/estimated according to AstraZeneca standards.

Pharmacokinetics analysis will, where data allow, be carried out using actual elapsed times determined from the PK sampling and dosing times recorded in the database. If actual elapsed times are missing, nominal times may be used. Nominal sampling times may be used for any agreed interim PK parameter calculations.

Where data allow, the following PK parameters for AZD1402 will be derived from serum concentrations:

Cmax	Maximum observed serum (peak) drug concentration
tmax	Time to reach peak or maximum observed concentration or response following drug administration
Ctrough	Observed lowest drug concentration reached before the next dose is administered (pre-dose)
λz	Terminal rate constant, estimated by log-linear least squares regression of the terminal part of the concentration-time curve
$t_{1/2\lambda z}$	Half-life associated with terminal slope (λz) of a semi-logarithmic concentration-time curve
AUClast	Area under the serum concentration-curve from zero to the last quantifiable concentration
AUC τ	Area under serum concentration-time curve in the dosing interval τ

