CL/F	Apparent total body clearance of drug from serum after extravascular administration
Vz/F	Volume of distribution (apparent) at steady state following extravascular administration (based on terminal phase)
Dose normalised AUC τ	Area under the serum concentration-time curve in the dosing interval τ divided by the dose administered
Dose normalised Cmax	Maximum observed serum (peak) drug concentration divided by the dose administered
Dose normalised AUClast	Area under the serum concentration-time curve from zero to the last quantifiable concentration divided by the dose delivered in mg
tlast	Time of last observed (quantifiable) serum concentration
Rac AUC	Accumulation ratio for AUC τ
Rac Cmax	Accumulation ratio for Cmax

The following diagnostic parameters for PK analysis will be provided:

λz lower	Lower (earlier) t used for λz determination
λz upper	Upper (later) t used for λz determination
λzN	Number of data points used for λz determination
Rsq	Statistical measure of fit for the regression used for λz determination
Rsq adj	Statistical measure of fit for the regression used for λz determination adjusted for the number of used data points (n obs)
λz span ratio	Time period over which λz was determined as a ration of $t_{1/2\lambda z}$

Additional PK parameters may be determined where appropriate.

Serum concentrations will be listed and summarised by treatment and PK day using appropriate descriptive statistics. Where possible, the following descriptive statistics will be presented: n, geometric mean, geometric coefficient of variation, geometric mean +geometric standard deviation, geometric mean -geometric standard deviation, arithmetic mean, arithmetic SD, median, minimum and maximum based on the PK analysis set. Serum concentrations that are BLQ will be handled as described in the SAP.

Combined individual serum concentration per dose level and PK day (spaghetti plots) will be presented in linear and semi-logarithmic scale with separate plots for each dose level and PK day. Figures for the geometric mean concentration-time data will be presented for all doses overlaid on the same plot for a given PK day, in both a linear and semi-logarithmic scale.

Figures for the geometric mean concentration-time data will also be presented for PK Days 1 and 28 overlaid on the same plot for a given dose level, in both a linear and semi-logarithmic scale.

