3.2.3 Pharmacokinetic Endpoints and Associated Variables

Blood samples for PK assessments will be collected from all the participants at timepoints mentioned in the SoA (Table 2 and Table 3).

Intense sampling will be performed in Part 2 of the study in a subset of approximately 20 participants per treatment arm at timepoints mentioned in the SoA (Table 2 and Table 3). The participants in these subsets may be asked to stay in the clinic overnight for logistical reasons depending on the sampling timepoints.

Pharmacokinetic analysis for AZD1402 from intense sampling profiles will be performed by bioanalytical test sites operated on behalf of AstraZeneca Research and Development.

Where data allow, the following PK parameters for AZD1402 will be derived from serum concentrations:

Cmax	Maximum observed serum (peak) drug concentration
tmax	Time to reach peak or maximum observed concentration or response following drug administration
Ctrough	Observed lowest drug concentration reached before the next dose is administered (pre-dose)
λ_z	Terminal rate constant, estimated by log linear least squares regression of the terminal part of the concentration-time curve
$t_{1/2}\lambda_z$	Half-life associated with terminal slope (λ_z) of a semi-logarithmic concentration-time curve
AUClast	Area under the serum concentration-curve from zero to the last quantifiable concentration
AUC τ	Area under serum concentration-time curve in the dosing interval τ
CL/F	Apparent total body clearance of drug from serum after extravascular administration
Vz/F	Volume of distribution (apparent) at steady state following extravascular administration (based on terminal phase)
Dose normalised AUC τ	Area under the serum concentration-time curve in the dosing interval τ divided by the dose administered in mg
Dose normalised Cmax	Maximum observed serum (peak) drug concentration divided by the dose delivered in mg
Dose normalised AUClast	Area under the serum concentration-curve from zero to the last quantifiable concentration divided by the dose delivered in mg
tlast	Time of last observed (quantifiable) serum concentration
Rac AUC	Accumulation ratio for AUC τ
Rac Cmax	Accumulation ratio for Cmax

Statistical Analysis Plan

The following diagnostic parameters for PK analysis will be provided:

λz lower	Lower (earlier) t used for λz determination
λz upper	Upper (later) t used for λz determination
λzN	Number of data points used for λz determination

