4.9.2 Treatment Compliance

Compliance will be assessed by checking the daily e-Diary and eCRF.

For all treatments, treatment compliance will be calculated as:

$$\text{Treatment compliance (\%)} = \frac{\text{Number of doses taken during treatment period}}{\text{Number of doses planned (28 days*) during treatment period}} \times 100.$$

*The number of doses planned is 55 since there is only 1 dose in the morning of Day 28.

Compliance is expected to be $\geq 80\%$ during the Treatment Period.

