4.15.3 Pharmacokinetic Parameters

Pharmacokinetic parameters will be calculated by non-compartmental analysis methods from the concentration-time data using Phoenix® WinNonlin® (Version 8.1) or higher following these guidelines:

- Concentration data will be used as supplied by the analytical laboratory for PK analysis. The units of concentration and resulting PK parameters, with the amount and concentration units, will be presented as they are received from the analytical laboratory.
- Cmax and tmax will be derived directly from the serum concentration-time profiles. For multiples peaks the highest post-dose concentration will be reported as Cmax. In the case that the multiple peaks are of equal magnitude, the earliest tmax will be reported.
- Serum concentrations which are BLQ from the time of pre-dose sampling ($t = 0$) up to the time of first quantifiable concentration will be set to a value of zero. After the first quantifiable concentration, any BLQ serum concentrations will be set to missing for all concentration profiles.
- Where 2 or more consecutive concentrations are BLQ at the end of a profile, the profile will be deemed to have terminated and therefore any further quantifiable concentrations will be set to missing for the calculation of the PK parameters unless there is a scientific rational not to do so, which will be documented in the CSR.
- Any embedded BLQ value (between 2 quantifiable concentrations) will be set to missing for the purposes of PK analysis.
- If an entire concentration-time profile is BLQ, the profile will be excluded from the PK analysis.
- Terminal elimination half-life, calculated as $(\ln 2)/\lambda_z$, will be estimated by log-linear LS regression of the terminal part of the concentration-time curve. The start of the terminal elimination phase for each subject will be defined by visual inspection and will be the first point at which there is no systematic deviation from the log-linear decline in serum concentrations. A minimum of 3 data points following Cmax and including the last measurable concentration will be used in calculating λ_z . The duration of time over which λ_z should, where possible, span 3 half-lives. The adjusted correlation coefficient (Rsq adj) should be ≥ 0.8 .

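### In Part 2, Day 1 intensive sampling ends at 8 h of a 12 h dosing interval, so Day 1 AUCτ and Rac AUC need extrapolation and cannot be obtained that way when the observed peak is at 3 h or later

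*Protocol*

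**What the plan says.** The protocol title describes "Inhaled AZD1402 Administered as a Dry Powder Twice Daily for Four Weeks". Both documents list AUCτ among the PK parameters; the definition in Protocol 9.4.4.1 is "Area under serum concentration-time curve in the dosing interval τ". Both also list Rac AUC, given there as "Accumulation ratio for AUC τ". PK parameters are a Part 2 secondary outcome, with sparse sampling in everyone and a full profile in a subset.

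Sampling differs between the Parts (Protocol 1.3):

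- **Part 1, Day 1** (Table 1, footnote z): pre-dose, 1, 2, 3, 4, 6 and 8 h, "and 12 h (up to 1h prior to the next dose, must be before the subsequent dose". Day 28 also has a 12 h sample.
- **Part 2, Day 1** (Table 2, footnote x): pre-dose, then "Timing of intense samples: Day 1: 1, 2, 3", 6 and 8 h. There is no 12 h sample. The next PK sample is at Visit 4 or Visit 5, depending on whether the footnote or the SAP's schedule grid is followed. Neither visit closes the first interval.
- **Part 2, Day 28** (same footnote): pre-dose, 1, 2, 3, 6, 8, 24, 48 and 96 h after a single last dose.

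For the terminal slope, SAP 4.15.3 states: "A minimum of 3 data points following Cmax and including the last measurable concentration will be used in calculating" λz. The fitted span should reach three half-lives where possible. AUC uses linear-up, log-down trapezoids and needs three consecutive quantifiable concentrations. The SAP does not say how to obtain AUCτ when the last sample falls before τ; parameters are derived where the data allow.

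**The concern.** On Part 2 Day 1 a third of the dosing interval has no data. Any Day 1 AUCτ, and hence any Rac AUC, must project from the 8 h sample to 12 h with λz. Whether λz can be estimated depends on when the participant peaks. Participants with a late observed peak cannot supply three later points, so they drop out of the accumulation summary.

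This loss is not random, because slower absorption goes with somewhat more accumulation. With only about 20 profiled participants expected in the main active arm, the reported accumulation could come from a small group selected for early peaks. The primary endpoint and the efficacy analyses are not touched.

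**Working it through.** **1. Dosing interval.** The SAP's own dose count confirms it. Section 4.9.2 says "The number of doses planned is 55 since there is only 1 dose in the morning of Day 28", and 2 × 28 − 1 = 55. Dosing is twice daily and τ = 12 h.

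**2. Size of the subset.** 25% of 80 = 20, which agrees with the approximately 20 per arm in SAP 3.2.3. For the arm of about 5, 25% is 1.25, so one participant at most. Placebo samples are not normally assayed (Protocol 8.5.1.3).

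**3. Points left after the observed peak, against the minimum of three.**

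| Observed tmax | Part 2 Day 1 | Part 2 Day 28 |
|---|---|---|
| 1 h | 4 | 7 |
| 2 h | 3 | 6 |
| 3 h | 2 | 5 |
| 6 h | 1 | 4 |
| 8 h | 0 | 3 |

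The Day 28 counts assume that all later samples are quantifiable. On Day 1 the rule fails from 3 h onward. Even with a peak at 1 or 2 h, the usable spans are 2 to 8 h and 3 to 8 h. The three-half-life target is then met only for half-lives up to 6/3 = 2.0 h or 5/3 = 1.7 h.

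**4. Unobserved share of Day 1 AUC(0-12 h).** The documents give no half-life or tmax, so both are assumptions here. The model is one-compartment with first-order absorption: C(t) ∝ exp(−k·t) − exp(−ka·t), with k = ln 2 / half-life and ka solved from tmax = ln(ka/k)/(ka − k).

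Worked case, half-life 4 h and tmax 2 h: k = 0.1733, ka ≈ 1.095.

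- AUC(0-12) ∝ (1 − 0.125)/0.1733 − 1/1.095 = 5.049 − 0.913 = 4.136.
- AUC(8-12) ∝ (0.25 − 0.125)/0.1733 = 0.721 (the absorption term is negligible).
- Share = 0.721/4.136 = 17.4%.

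| Assumed half-life | tmax 1 h | tmax 2 h | tmax 3 h |
|---|---|---|---|
| 2 h | 5.7% | 9.3% | not attainable |
| 4 h | 15.3% | 17.4% | 21.4% |
| 6 h | 20.5% | 22.1% | 24.7% |
| 12 h | 26.7% | 27.8% | 29.3% |

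**5. Profiles lost.** Profiles were simulated at 1, 2, 3, 6 and 8 h with assumed lognormal variation (SD 0.4 for ka, 0.3 for k, 0.15 residual). A profile counts as lost if its highest value is at 3 h or later.

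| Assumed half-life | tmax 1 h | tmax 2 h | tmax 3 h |
|---|---|---|---|
| 2 h | 2% | 30% | not attainable |
| 4 h | 7% | 33% | 63% |
| 12 h | 24% | 43% | 66% |

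With 20 profiles and a 33% loss, 20 × 0.67 ≈ 13 remain. At half-life 4 h and tmax 2 h, mean true accumulation is about 1.25 in the lost profiles and just under 1.2 in those kept.

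**6. An alternative from the same samples.** In the worked case, steady state by superposition gives:

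- AUC over τ ∝ 1/0.1733 − 1/1.095 = 4.858, so the true ratio is 4.858/4.136 = 1.17.
- Day 1 AUC(0-8) ∝ 4.136 − 0.721 = 3.415.
- Steady-state AUC(0-8) ∝ (0.75/0.1733)/0.875 − 0.913 = 4.033.
- The 0-8 h ratio is 4.033/3.415 = 1.18.

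For half-lives of 4 to 12 h and tmax of 1 to 3 h, the 0-8 h ratio stays within about 3% of the 12 h ratio (from 1.15 against 1.15 to 2.18 against 2.13) and needs no λz.

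**The case against.** Several points on the other side stand.

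- **Extrapolation need not mean bias.** In the same model, with λz fitted to 3, 6 and 8 h, tmax 1 to 2 h and half-life 4 to 12 h, the extrapolated Day 1 AUC(0-12) is within 0.5% of the truth. Where λz is estimable the projection is sound if the decline is mono-exponential. The weakness is selective loss more than error in the values kept.
- **The half-life may be short.** The protocol's amendment history calls it short, without a figure. At about 2 h or less with a peak at 1 to 2 h, under 10% is unobserved. Loss of profiles can still reach about 30% if tmax is near 2 h.
- **Unseen rules may apply.** Protocol 9.4.4.1 refers to sponsor standards for PK calculation, which could contain an extrapolation rule. Sampling times may be amended and further parameters are permitted. None of this selects a method in the plan as written.
- **PK is secondary and descriptive.** Rac Cmax, trough plots and the Part 1 profiles also inform accumulation.

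A reader might also infer that Rac AUC will be overstated by 18% to 42%. That follows only if Day 1 AUC to 8 h is divided into Day 28 AUCτ. No section plans this, and AUClast is a separate parameter. Nor is it right that slow absorbers have the largest accumulation. In the model elimination dominates: at half-life 4 h the ratio moves from 1.15 to 1.22 as tmax goes from 1 to 3 h, while at tmax 1 h it moves from 1.15 to 2.03 as half-life goes from 4 to 12 h.

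**Conclusion.** The point holds for Part 2 Day 1 AUCτ and Rac AUC in the intensive-sampling subset, and no further. There, both quantities need extrapolation over the last 4 of 12 h, and the SAP's three-point rule rules out that route once the observed Day 1 peak is at 3 h or later. These facts come from the documents alone.

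It would be tempting to conclude that AUCτ is compromised for every participant. The documents do not support that. Part 1 has its 12 h sample. Part 2 Day 28 AUCτ can be interpolated between 8 and 24 h, also for late peakers, unless the 24 h value is below quantification and set to missing. Rac Cmax needs no 12 h sample.

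The size is uncertain because half-life and tmax are not given. With half-life 2 to 12 h and tmax 1 to 3 h in a one-compartment model, about 6% to 29% of Day 1 AUC(0-12) is unobserved and about 2% to 66% of profiles are lost, with modestly higher accumulation among those lost. This is worth correcting because the remedy is cheap, but it does not threaten the trial's main conclusions.

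**What to change.** In SAP 3.2.3 and 4.15.3:

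- Add AUC(0-8 h) on Day 1 and Day 28, and their ratio, as the main Part 2 accumulation measure.
- Show the same 0-8 h ratio for Part 1, whose samples allow it. This makes the Parts comparable and lets the 0-8 h ratio be checked against the 12 h ratio.
- Keep Part 2 Day 1 AUCτ and Rac AUC as supportive results where λz is estimable, and state that they are obtained by λz extrapolation from 8 to 12 h.
- Report how many profiles qualify for each measure.

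The cost is SAP wording and one partial-AUC setting in the PK software, with no extra blood sample. This suits a SAP already revised for anticipated closure. The downside is one more parameter and a Part 2 ratio defined over 8 h. That ratio will not be available for every profiled participant either: it still needs enough quantifiable concentrations under the SAP's below-quantification and three-consecutive-value rules.
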